18.2 Translational Medicine Procedures

Whole exome sequencing to analyze mutational load: To test whether there is a correlation of tumor mutational load and response to PD-1 antibody therapy, DNA will be isolated from thick slides of FFPE tissues and *PBMC via commercial kit (i.e. Qiagen AllPrep DNA/RNA FFPE kit, cat 80234). Whole exome sequencing (WES), including probe-based exon capture, library preparation, and high throughput 100bp paired-end sequencing on the Illumina HiSeq2500 platform will be performed at the UCLA Immunogenetics core laboratory (CLIA approved lab). DNA from the same patient's PBMC (preferably) or other non-cancerous tissue will be isolated and sequenced for baseline comparison and differentiation of germline SNPs from true somatic mutations. Read mapping and data preprocessing will be performed according to the Broad Institute Best Practices Guidelines for the Genome Analysis Toolkit (version 3), and mutation detection will require a consensus call among several published programs (Varscan2, MuTect, GATK HaplotypeCaller). Mutational load will be quantified as the number of nonsynonymous somatic mutations per MB.

Quantitative analysis of T cell infiltration: To analyze whether baseline CD8+ cell infiltration is correlated with response to anti-PD1 therapy, and whether PD-1 blockade can increase CD8+ cell infiltration in DM patients, slides taken from standard formalin-fixed paraffin-embedded (FFPE) tissue blocks obtained from baseline, 4 week (on treatment), and 9 week biopsies will be stained by immunohistochemistry (IHC) for S100 and CD8 to determine the presence of CD8+ T cells inside tumors and in the invasive margin. Slides will be analyzed using quantitative digital pathology following the methods described (10). This analysis will provide a predictive score for response or lack of response to pembrolizumab based on the baseline CD8+ T cell infiltration.

Method: Slides will be stained with S100 and CD8 (one slide per stain) at the UCLA Anatomic Pathology IHC Laboratory (CLIA approved lab). Immunostaining will be performed on Leica Bond III autostainers using Leica Bond ancillary reagents and REFINE polymer DAB detection system (Leica DS9800). Antibodies used will include rabbit polyclonal S100 (DAKO, 1/1,000 dilution, low pH retrieval), mouse anti-CD8 clone C8/144B (DAKO, 1/100, low PH retrieval), and all staining will be performed on Dako autostainers, and visualized with DAB. Slides will be baked for 60 minutes at 60°C. Procedure involves dewaxing, heat-retrieved in Bond ER1 (pH6) buffer for 20 minutes, and sequential incubations with primary antibody, post-primary reagent, and polymer for 15 minutes, 8 minutes, and 8 minutes, respectively, and subsequent DAB chromogen application and Hematoxylin counterstaining. All stained slides will be evaluated in a blinded fashion by one dermatopathologist and one investigator trained to identify the features of melanoma, and the presence of CD8 within the tumor parenchyma (tumor) and the connective tissue surrounding the tumor (invasive margin) will be examined.

All slides will be scanned at an absolute magnification of X200 (resolution of 0.5 mm/pixel). An algorithm was designed based on pattern recognition that quantified immune cells within S100-positive areas (tumor) and S100-negative areas (invasive margin). Image analysis based on RGB (red, green, blue) spectra will be used to detect all cells by counterstaining with haematoxylin (blue), and DAB or fast red. The algorithm calculated the density (cells mm⁻²) and percentage cellularity (% positive cells/all nucleated cells) using Indica Labs Halo platform.

Analysis of TCR clonality in tumors: To answer the question whether the T cell response is targeting specific tumor antigen (mono-clonal) or a non-specific process (poly-clonal) in the tumors, we will analyze TCR clonality by deep sequencing the TCR Vβ CDR region using the ImmunoSeq assay from Adaptive Biotech as described (10). From thick slides of

FFPE tissues taken at baseline, 4 weeks, and 9 weeks, we will isolate DNA and submit it for TCR V β sequencing. This analysis will provide information about the clonality or diversity of T cells infiltrating tumors in DM samples. DNA analysis will be performed by the UCLA Immunogenetics core laboratory (CLIA approved lab).

DNA will be isolated from FFPE thick cuts followed by extraction using a DNeasy kit (Qiagen). Melanin will be removed from visibly pigmented melanoma samples using a PCR Inhibitor Removal kit (ZymoResearch). TCR V β CDR3 regions will be amplified and sequenced using the survey ImmunoSeq assay in a multiplexed PCR method using 45 forward primers specific to TCR V β gene segments and 13 reverse primers specific to TCR V β gene segments (Adaptive Biotechnologies). Reads of length 87bp will be obtained using the Illumina HiSeq System. For each sample, Shannon entropy will be calculated on the clonal abundance of all productive TCR sequences in the data set. Shannon entropy will be normalized to the range by dividing Shannon entropy by the logarithm of the number of unique productive TCR sequences in the data set. This normalized entropy value will be then inverted (12 normalized entropy) to produce our clonality metric.

Analysis of adaptive immune resistance mechanism in tumors: Slides taken from standard FFPE tissue blocks obtained from baseline, and the on treatment biopsy will be stained by immunohistochemistry (IHC) for PD-L1 (SP142, Spring Bioscience) to evaluate whether PD-L1 can be induced by PD-1 blockade, and which it is correlated with response. Slides will be analyzed using quantitative digital pathology following the methods described for Quantitative analysis of T cell infiltration. Analysis will be performed at the UCLA Anatomic Pathology IHC Laboratory (CLIA approved lab).

Method:

1. Bake slides for 1 hour at 65°C.
2. Deparaffinize slides in xylene (3 changes) and rehydrate through graded ethanol to deionized-H₂O.
3. Perform antigen retrieval in pressure cooker for 5 minutes with Tris-EDTA pH9 buffer (Leica ER2). Cool for 15 minutes at room temperature and rinse in DI-water.

Perform IHC on Leica Bond III autostainer with Refine Polymer Detection (Leica DS9800); autostainer was programmed for primary antibody at 1/200 dilution in daVinci Green Diluent (Biocare Medical) for 60 minutes, Polymer for 15 minutes, Peroxidase block for 5 minutes, DAB for 10 minutes, and offline manual steps 0.5% cupric sulfate for 10 minutes and Hematoxylin for 5 minutes. Usual Bond washes between steps. Use Bond Refine Polymer Detection kit (DS9800), which includes reagents for all steps after primary antibody, except for cupric sulfate and hematoxylin counterstain.

18.3 Management of Immune-Related Adverse Events, Diarrhea, Hepatotoxicity, Endocrinopathy, and Neuropathy for Ipilimumab *

[figure not shown]
*Investigator's Brochure (2011)

General Recommendations for Management of Suspected Inflammatory Events

Caution: With the appearance of any generalized rash, discontinue and avoid any concomitant medications (e.g. antibiotics, anticonvulsants, or proton pump inhibitors) that may be associated with severe skin reactions

+ Definition: irAEs are associated with ipilimumab exposure and are consistent with immune phenomenon

[figure not shown]
Examples of possible irAEs (*common and rare*): rash, pruritus, diarrhea/colitis, hepatitis/elevated liver function tests, hypopituitarism, hypo/hyperthyroidism, uveitis, pneumonitis, nephritis, pancreatitis, aseptic meningitis, toxic epidermal necrolysis, myopathy/myositis or neuromuscular disorder (e.g. Myasthenia gravis, Guillain-Barre Syndrome)

* Based on clinical experience to date, systemic steroids for treatment of irAEs do not appear to impact the development or maintenance of ipilimumab clinical activity in advanced melanoma.

Diarrhea Management Algorithm

Hepatotoxicity Management Algorithm

[figure not shown]
Situation: rising liver function tests (LFTs) >8X ULN or suspected immune-mediated Hepatitis

[figure not shown]
- 1) Admit subject to hospital for evaluation and close monitoring
- 2) Stop further ipilimumab dosing until hepatotoxicity is resolved. Consider permanent discontinuation of ipilimumab per protocol
- 3) Start at least 120 mg methylprednisolone sodium succinate per day, given IV as a single or divided dose
- 4) Check liver laboratory test values (LFTs, T-bilirubin) daily until stable or showing signs of improvement for at least 3 consecutive calendar days
- 5) If no decrease in LFTs after 3 calendar days or rebound hepatitis occurs despite treatment with corticosteroids, then add mycophenolate mofetil 1g BID per institutional guidelines for immunosuppression of liver transplants (supportive treatment as required, including prophylaxis for opportunistic infections per institutional guidelines)
- 6) If no improvement after 5 to 7 calendar days, consider adding 0.10 to 0.15 mg/kg/day of tacrolimus (trough level 5-20 ng/mL)
- 7) If target trough level is achieved with tacrolimus but no improvement is observed after 5 to 7 calendar days, consider infliximab, 5 mg/kg, once
- 8) Continue to check LFTs daily for at least 2 weeks to monitor sustained response to treatment

A flow chart of the algorithm is depicted on the following page.

Hepatotoxicity Management Algorithm

[figure not shown]

Footnote

For numbered footnotes (^{1,2,3,4}), please refer to further explanation and text found in the corresponding dotted line boxes to the right side of the algorithm

Neuropathy Management Algorithm

[figure not shown]
18.4 Management of Algorithms for Endocrinopathy, Gastrointestinal, Hepatic Neurological, Pulmonary, Renal, and Skin Adverse Events for Nivolumab

CLOSED EFFECTIVE 07/15/2020

Endocrinopathy Management Algorithm

[figure not shown]
Rule out non-inflammatory causes. If non-inflammatory cause, treat accordingly and continue immuno-oncology (I-O) therapy.
 Consider visual field testing, endocrinology consultation, and imaging.

Patients on IV steroids may be switched to an equivalent dose of oral corticosteroids (e.g. prednisone) at start of tapering or earlier, once sustained clinical improvement is observed. Lower bioavailability of oral corticosteroids should be taken into account when switching to the equivalent dose of oral corticosteroids.

GI Adverse Event Management Algorithm

Rule out non-inflammatory causes. If non-inflammatory cause is identified, treat accordingly and continue I-O therapy. Opiates/narcotics may mask symptoms of perforation. Infliximab should not be used in cases of perforation or sepsis.

[figure not shown]

Patients on IV steroids may be switched to an equivalent dose of oral corticosteroids (e.g. prednisone) at start of tapering or earlier, once sustained clinical improvement is observed. Lower bioavailability of oral corticosteroids should be taken into account when switching to the equivalent dose of oral corticosteroids.

Hepatic Adverse Event Management Algorithm

Rule out non-inflammatory causes. If non-inflammatory cause, treat accordingly and continue I-O therapy. Consider imaging for obstruction.

[figure not shown]
Patients on IV steroids may be switched to an equivalent dose of oral corticosteroids (e.g. prednisone) at start of tapering or earlier, once sustained clinical improvement is observed. Lower bioavailability of oral corticosteroids should be taken into account when switching to the equivalent dose of oral corticosteroids.

I-O therapy may be delayed rather than discontinued if AST/ALT ≤ 8 x ULN and T.bili ≤ 5 x ULN.

The recommended starting dose for grade 4 hepatitis is 2 mg/kg/day methylprednisolone IV.

Neurological Adverse Event Management Algorithm

Rule out non-inflammatory causes. If non-inflammatory cause, treat accordingly and continue I-O therapy.

[figure not shown]

Patients on IV steroids may be switched to an equivalent dose of oral corticosteroids (e.g. prednisone) at start of tapering or earlier, once sustained clinical improvement is observed. Lower bioavailability of oral corticosteroids should be taken into account when switching to the equivalent dose of oral corticosteroids.

Pulmonary Adverse Event Management Algorithm

[figure not shown]
Rule out non-inflammatory causes. If non-inflammatory cause, treat accordingly and continue I-O therapy. Evaluate with imaging and pulmonary consultation.

Patients on IV steroids may be switched to an equivalent dose of oral corticosteroids (e.g. prednisone) at start of tapering or earlier, once sustained clinical improvement is observed. Lower bioavailability of oral corticosteroids should be taken into account when switching to the equivalent dose of oral corticosteroids.

Renal Adverse Event Management Algorithm

Rule out non-inflammatory causes. If non-inflammatory cause, treat accordingly and continue I-O therapy

[figure not shown]

Patients on IV steroids may be switched to an equivalent dose of oral corticosteroids (e.g. prednisone) at start of tapering or earlier, once sustained clinical improvement is observed. Lower bioavailability of oral corticosteroids should be taken into account when switching to the equivalent dose of oral corticosteroids.

Skin Adverse Event Management Algorithm

Rule out non-inflammatory causes. If non-inflammatory cause, treat accordingly and continue I-O therapy.

Patients on IV steroids may be switched to an equivalent dose of oral corticosteroids (e.g. prednisone) at start of tapering or earlier, once sustained clinical improvement is observed. Lower bioavailability of oral corticosteroids should be taken into account when switching to the equivalent dose of oral corticosteroids. Refer to NCI CTCAE v4 for term-specific grading criteria.

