8.3 Dose Delay Criteria Ipilimumab (Arm 1)

Dose modifications for ipilimumab by adverse event type are detailed in [Table 8.1](#). General considerations for dose modifications are as follows.

- a. It is necessary to avoid study drug dosing and initiate appropriate evaluation and/or treatment for the following adverse events:
- Any \geq Grade 3 skin related adverse event regardless of causality.
 - Any \geq Grade 2 non-skin related adverse event (including immune-mediated adverse reactions), except for easily corrected laboratory abnormalities that do not reflect underlying organ pathology.
 - Any \geq Grade 3 laboratory abnormality.
 - Any adverse event, laboratory abnormality or intercurrent illness that, in the opinion of the treating investigator, presents a substantial clinical risk to the patient with continued dosing.
 - It may be necessary to hold study drug to evaluate Grade 1 events that suggest ongoing or incipient autoimmune disease including GI toxicity, diarrhea, pancreatitis, hepatitis, pituitary insufficiency, early evidence of neurologic events, skin toxicity until diagnosis and progression are determined.
- b. Ipilimumab may be restarted if/when the adverse event(s) resolve(s) in severity or returns to baseline within 2 weeks of initial dose administration:
- If the adverse event has been determined not be related to ipilimumab or is not an autoimmune/inflammatory event. If more than 1 dose is to be skipped or > 2 week delay is expected due to current events not related to study the dosing schedule modifications must be discussed with the study chairs prior to implementation.
 - If the *adverse event has resolved to \leq Grade 1*, ipilimumab dosing may be restarted at the next scheduled timepoint per protocol. Please follow guidelines for specific events. Please note that re-initiating treatment may be associated with recurrence or exacerbation of autoimmune or inflammatory events. In some instances clinical resolution of events such as colitis may be associated with residual pathologic changes and should require evaluation of complete resolution prior to restarting therapy.
 - If the adverse event has not resolved in the protocol-specified dosing window (3 weeks [± 3 calendar days]), the next scheduled dose will be skipped and dosing will be resumed at the subsequently scheduled dose.

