 - Events which require intervention with immunosuppressant therapy, steroids, surgery, or hormone replacement generally require permanently stopping study treatment.
- c. Permanently discontinue ipilimumab for any of the following:
- Persistent adverse reactions that require holding more than 2 treatment doses.
 - Any related Grade 3 or 4 event (see exceptions below)
 - Any event that requires immunosuppressive treatment or systemic steroids which cannot be discontinued during the time in which it takes to hold more than 2 treatment doses
 - Severe or life-threatening adverse reactions, including any of the following:
 - Colitis with abdominal pain, fever, ileus, or peritoneal signs; increase in stool frequency (7 or more over baseline), stool incontinence, need for IV hydration for more than 24 hours, gastrointestinal hemorrhage, and gastrointestinal perforation

- Aspartate aminotransferase (AST) or alanine aminotransferase (ALT) >5 times the upper limit of normal or total bilirubin >3 times the upper limit of normal
- Stevens-Johnson syndrome, toxic epidermal necrolysis, or rash complicated by full thickness dermal ulceration, or necrotic, bullous, or hemorrhagic manifestations
- Severe motor or sensory neuropathy, Guillain-Barré syndrome, or myasthenia gravis
- Severe immune-mediated reactions involving any organ system (e.g., nephritis, pneumonitis, pancreatitis, non-infectious myocarditis)
- Immune-mediated ocular disease that is unresponsive to topical immunosuppressive therapy
- Any adverse event, laboratory abnormality or intercurrent illness which, in the judgment of the investigator, presents organ specific injury and/or a substantial clinical risk to the patient with continued dosing.

NOTE: The following neurological adverse events require permanent discontinuation of ipilimumab and define unacceptable neurotoxicity:

- Any motor neurologic toxicity \geq Grade 3 regardless of causality
- Any \geq Grade 3 treatment related sensory neurologic toxicity

Please refer to [Appendix 18.3](#) and [Appendix 18.4](#) for specific treatment algorithms.

- d. Exceptions to Permanent Discontinuation of Ipilimumab
- Potentially reversible inflammation (< Grade 4), attributable to a local anti-tumor reaction and a potential therapeutic response. This includes inflammatory reactions at sites of tumor resections or in draining lymph nodes, or at sites suspicious for, but not diagnostic of metastasis.

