 - Hospitalization for \leq Grade 2 adverse events where the primary reason for hospitalization is to expedite the clinical work-up.
 - Patients with the following conditions where in the treating investigator's opinion continuing study drug administration is justified based on the potential for continued clinical benefit:
 - Patients treated with systemic steroids for less than 2 weeks without evidence of autoimmune disease requiring steroids treatment
 - Grade 2 skin rash treated with topical steroids for less than 4 weeks
 - Grade 2 ocular toxicity that has completely responded to topical therapy within 4 weeks
 - Endocrinopathies where clinical symptoms are controlled with appropriate hormone replacement therapy. **Note:** Ipilimumab may not be restarted while the patient is being treated with systemic corticosteroids except for patients on stable doses of hormone replacement therapy such as hydrocortisone.
- e. Allowance for ipilimumab dose delay
- In general, patients who meet criteria to resume ipilimumab will also have met criteria to resume nivolumab with ipilimumab, so it should be feasible to synchronize dosing of both drugs when resuming ipilimumab. In order to facilitate this, the dosing calendar days of nivolumab and ipilimumab may be adjusted within a +/- 5 day window, as long as consecutive nivolumab doses are given at least 12 calendar days apart.
 - If an ipilimumab dose is delayed beyond 6 weeks from the prior ipilimumab dose, then subsequent nivolumab doses should be rescheduled to maintain at least a 3-week interval between consecutive ipilimumab doses.

- Dosing delays to manage drug-related adverse events, such as prolonged steroid tapers, are allowed. Disease assessments should continue as per protocol even if dosing is delayed.
- Dosing delays resulting in no ipilimumab dosing for > 6 weeks that occur for non-drug-related reasons may be allowed if approved by the Study Chairs. Disease assessments should continue as per protocol even if dosing is delayed.
- In event of any Grade 2 adverse event experienced while on combination nivolumab plus ipilimumab therapy, patient may resume treatment/may be continued on nivolumab monotherapy alone, at the discretion of the treating investigator
- Ipilimumab will not be given as monotherapy for Arm 2.

NOTE: If adverse events result in permanent discontinuation of ipilimumab, then subsequently manage dose delays under Management/Next Dose for nivolumab alone

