8.4 Dose Delay Criteria for Nivolumab in Combination with Ipilimumab (Arm 2)

Dose modifications for nivolumab in combination with ipilimumab by adverse event type are detailed in [Table 8.1](#). General considerations for dose modifications are as follows.

For the initial induction period, patients with Grade 2 or 3 events requiring discontinuation of treatment with the combination may consider continuing treatment with single agent nivolumab when the event resolves to baseline. However, patients with renal, CNS, or pulmonary toxicity must be removed from study.

- a. In addition to the AEs identified in the table below, ipilimumab and nivolumab dose should be delayed for any AE, laboratory abnormality or inter-current illness which, in the judgment of the treating investigator, warrants delaying the dose of study medication.
- b. Patients requiring a delay of > 6 weeks or who experience immune-related toxicity with inability to decrease prednisone ≤ 10 mg PO daily must go off protocol therapy entirely.
- c. Patients who received systemic corticosteroids for management of any drug-related immunologic toxicity must be off corticosteroids or have tapered down to an equivalent dose of prednisone 10 mg/day.
- d. Nivolumab monotherapy may be continued at treating investigator discretion if there is evidence of clinical benefit. In this event, patient will continue nivolumab until AE is resolved and ipilimumab may be re-started or if ipilimumab is permanently discontinued (in congruence with guidelines in table below), then patient will continue nivolumab alone until cycles are completed. At completion of 4 cycles, patient may continue on nivolumab alone, as per protocol. If ipilimumab is permanently discontinued prior to receipt of 4 doses, nivolumab dosing should remain at the Cycle 1-4 dosing (1 mg/kg every 2 weeks) until completion of Cycle 4 and should then switch to Cycle 5+ dosing (480 mg every 4 weeks).

Table 8.1 Dose Modification for Related Adverse Events

Treatment-related Adverse Event	Grade of Event	Nivolumab and/or Ipilimumab
Nausea	≤ Grade 1	No dose modification
	Grade 2	Hold until ≤ Grade 1 OR baseline (exceptions as noted below) ¹
	Grade 3	Off protocol therapy (exceptions as noted below) ¹
	Grade 4	Off protocol therapy
*Patients requiring a delay of >2 weeks must go off protocol therapy.		
Recommended management: antiemetics.		
Diarrhea (immune-related enterocolitis)	≤ Grade 1	No dose modification

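### In Arm 1, Section 8.3c stops ipilimumab permanently above AST/ALT 5x or bilirubin 3x ULN, while a sentence in Appendix 18.4, to which 8.3c refers, allows delay up to 8x and 5x; no text says which prevails

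*Combined protocol and SAP*

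**What the plan says.** **Section 8.3 (headed for ipilimumab, Arm 1).** Item c lists the events for which ipilimumab must be stopped permanently. One entry is "Aspartate aminotransferase (AST) or alanine aminotransferase (ALT) >5 times the upper limit of normal or total bilirubin >3 times the upper limit of normal". Item c also stops the drug for any related Grade 3 or 4 event, subject to item d, and no exception in item d is framed in terms of liver tests. Item c closes with a cross-reference: "Please refer to [Appendix 18.3](#) and [Appendix 18.4](#) for specific treatment algorithms".

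**Restart and delay within 8.3.** Under item b, once an event has resolved to Grade 1 or less, "ipilimumab dosing may be restarted at the next scheduled timepoint per protocol". Item b also says: "Events which require intervention with immunosuppressant therapy, steroids, surgery, or hormone replacement generally require permanently stopping study treatment". Item e says: "Dosing delays to manage drug-related adverse events, such as prolonged steroid tapers, are allowed". Although 8.3 is headed Arm 1, item e contains rules for the combination arm, such as "Ipilimumab will not be given as monotherapy for Arm 2".

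**Rules by grade.** Both 8.3 and 8.4 point to Table 8.1 for dose modifications. Its column covers nivolumab and/or ipilimumab, and its liver row takes Grades 3 and 4 off protocol therapy. The row then names the hepatic algorithm as recommended management. Section 8.7 permanently discontinues both drugs at Grade 3 to 5 hepatotoxicity.

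**Appendix 18.4, Hepatic Adverse Event Management Algorithm.** The appendix is titled for nivolumab. The printed note under the hepatic flow chart reads: "I-O therapy may be delayed rather than discontinued if AST/ALT ≤ 8 x ULN and T.bili ≤ 5 x ULN". The endocrinopathy algorithm in the same appendix spells out I-O as immuno-oncology.

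**Appendix 18.3 (ipilimumab), Hepatotoxicity Management Algorithm.** Step 2 halts ipilimumab until resolution and says that permanent discontinuation should be considered, per protocol.

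**The concern.** The 18.4 sentence concerns dosing, not supportive care: it says when treatment may be delayed instead of discontinued. Its ceilings lie above the limits at which 8.3c makes stopping mandatory, and 8.3c itself sends the reader to that appendix. A site that follows the cross-reference could take the sentence as permission to delay ipilimumab, and later resume it, in an Arm 1 patient whom 8.3c requires to stop for good.

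The stake is patient safety. Section 8.7 notes that hepatic failure with ipilimumab has been fatal in clinical trials. Two sites could also treat the same laboratory result differently and each cite the protocol.

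**Working it through.** The plan states no figure to reproduce here. The check sets the two rules side by side.

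**Inputs.** Let A be the higher of AST and ALT, and B total bilirubin, both in multiples of ULN.

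- Stop rule, Section 8.3c: stop if A > 5 or B > 3.
- Delay permission, Appendix 18.4: may delay if A ≤ 8 and B ≤ 5.
- Clash: both conditions true.

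**Clash region.** Combining the two gives A ≤ 8 and B ≤ 5, with A > 5 or B > 3.

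| A | B | 8.3c | 18.4 sentence | Result |
|---|---|---|---|---|
| 6 | 1 | stop | may delay | clash |
| 4 | 4 | stop | may delay | clash |
| 6 | 4 | stop | may delay | clash |
| 8 | 5 | stop | may delay | clash |
| 5 | 3 | no stop | may delay | none |
| 5 | 2.5 | no stop | may delay | none |
| 6 | 6 | stop | no permission | none |
| 9 | 1 | stop | no permission | none |

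The 18.4 ceilings are 8/5 = 1.60 times the 8.3c limit for AST/ALT and 5/3 = 1.67 times the limit for bilirubin. These ratios describe the wording, not a risk.

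**Position relative to entry.** Section 5.3e admits AST and ALT up to 5x and bilirubin up to 2.5x the institutional ULN (Gilbert's syndrome excepted). The gap from entry ceiling to stop limit is 5 − 5 = 0 for AST/ALT and 3 − 2.5 = 0.5 for bilirubin. The region therefore adjoins the entry ceiling.

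**Does the 18.4 sentence reach Arm 1 ipilimumab?** The appendix title points to nivolumab, which Arm 1 does not receive. Three things point the other way:

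1. The sentence uses a generic term and names no agent.
2. The ipilimumab section, 8.3c, cites Appendix 18.4 alongside 18.3.
3. The Table 8.1 liver row covers either drug, and the algorithm name it cites matches the title in 18.4, not the one in 18.3.

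**Does the same numeric clash hold in Arm 2?** Section 8.4 prints no numeric liver limit. The rule there is by grade (Table 8.1 and 8.7), and the documents do not print the grade cut-offs. Whether A = 6 requires stopping in Arm 2 cannot be settled from the documents.

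**Do other rules close the gap?** They narrow it. Section 8.3b requires resolution to Grade 1 or less before restart and generally ends treatment when steroids are needed. But that rule is hedged, and 8.3e allows delays for long steroid tapers. In Arm 2, 8.4b ends protocol therapy for patients needing a delay of more than "6 weeks or who experience immune-related toxicity with inability to decrease prednisone" to 10 mg daily or less.

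**The case against.** The strongest reply is that Section 8 plainly governs. It gives the stop rule several times: the numeric limit and the Grade 3 or 4 rule in 8.3c, the liver row of Table 8.1, and 8.7. Dose modifications are said to be in Table 8.1, which cites the hepatic algorithm only as recommended management. The 18.4 sentence is permissive, so a site that stops ipilimumab complies with both texts. It also sits in a nivolumab appendix, as a note to a flow chart that is not shown and whose boxes might carry their own stop instruction.

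Much of this stands. It makes the Section 8 reading the likelier one, limits confidence, and makes the matter minor. It does not remove the inconsistency, because no text states the precedence for the hepatic algorithm. Footnote 5 of Table 8.1 comes closest: it separates recommended management from treatment management. But it is attached to the renal and lipase rows and names 18.3, not 18.4.

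Two stronger readings are tempting, and the documents support neither:

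- **That the 8.3c numbers also bind in Arm 2**, because 8.3e contains combination-arm rules. No text extends the 8.3c limits to Arm 2.
- **That many patients would fall in the clash region**, because it adjoins the entry ceiling. Eligibility ceilings are not a distribution of values, and the documents give no event rate.

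**Conclusion.** The inconsistency is real but narrow. For ipilimumab in Arm 1, the 8.3c stop and the 18.4 permission to delay give opposite answers in the clash region defined above. In Arm 2 the liver row cites the same algorithm, but no numeric clash is shown.

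The conclusion rests on the printed 18.4 sentence without its flow chart, and on reading its generic term as including ipilimumab, which the 8.3c cross-reference supports. Confidence is medium. The number of patients affected cannot be stated.

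A reader might infer that Appendix 18.3 has the same defect because step 2 only asks sites to consider permanent discontinuation. It does not: the step defers to the protocol, and so to Section 8. Nor does any of this bear on endpoints, power or the analysis. It is a minor, low-cost correction to safety wording.

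**What to change.** 1. At the head of Appendices 18.3 and 18.4, add: *Section 8 governs dosing, delay and discontinuation; the appendices give supportive management only.*
2. After the hepatic sentence in 18.4, add: *This does not override the discontinuation rules in Section 8 (8.3c for ipilimumab in Arm 1; Table 8.1 and 8.7 for both arms).*
3. Notify sites.

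The qualifier should keep its reference to Arm 1. A line applying the 5x and 3x limits to ipilimumab without naming the arm would carry the 8.3c numbers into Arm 2, which is a change of treatment policy and not a clarification. Step 2 of 18.3 needs no edit.

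The cost is two header lines, one qualifying sentence and a notice. Section 8 policy, sample size, visits and analysis stay as they are. The pages are stamped closed and ipilimumab is limited to four cycles, so few or no patients may still be receiving it. If so, the correction still helps in judging past dosing deviations and in any reuse of the appendix.
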